#### **4) Entry Criteria**

##### **Inclusion criteria**

- a) Age >18
- b) Enterocutaneous fistula (ECF) that could be secondary to volvulus, injury, prior trauma or surgery, or vascular ischemia

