### **Enrollment within 2 months of signing consent**

Inclusion/Exclusion criteria

Vital signs measurements

Nutritional assessment

3-day average fistula output

Complete questionnaires (see additional documents):

1. ASCQ-Me Short Form v2.0 - Social Functioning Impact
2. ASCQ-Me v2.0 - Sleep Impact Short Form

IRB Study Number: 20170189  
Version Date: June 16, 2021  
PI: [name]

NCT02889393

3. Global Health Scale v1.2
4. PROMIS Scale v1.0 - GI Belly Pain
5. PROMIS Scale v1.0 - GI Diarrhea
6. PROMIS Scale v1.0 - GI Nausea and Vomiting
7. PROMIS SF v2.0 - Ability to Participate

Teaching of self-administration of medication

After study enrollment, the subject will be randomly assigned (by a computerized method, using the site 'www.sealedenvelope.com') to begin teduglutide treatment immediately or to continue standard of care (SOC) treatment. The randomization will be performed by a member of the study that is not involved in the informed consent process, and will be enclosed in sequentially numbered opaque envelopes. The envelopes will be given to the PI prior to the enrollment visit. At study visit 5 (day 56), the subject will then cross-over to the opposite treatment assignment. The half-life of teduglutide is 2-3 hours. During the period the subjects are on the "SOC only" treatment arm, the subjects will be given the option to replace some Study visits with Telephone Calls for their convenience. If study visits overlap due to the time window, either visit may be skipped or completed on the same day. Please see information below, and the Study schema.

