**Study Visit 10, End of Treatment (EOT), (Day 112) (+/- 1 week)**

Collect physical examination  
Collect Vital Signs measurements  
Chemistry Panel (sodium, potassium, chloride, bicarbonate, blood urea nitrogen, creatinine glucose)  
Liver Function tests (total bilirubin, direct bilirubin, alkalkine phosphatase, alanine aminotransferase, aspartate aminotransferase, lipase, amylase)  
Plasma PK (Pharmacokinetics)

- Processed according to separate "Sample Processing Procedure"

Serum pregnancy test  
Monitor severe adverse events (SAE) and adverse events (AE)  
Collect Concomitant medication review  
Collect Nutritional Assessment  
3-day average fistula volume (3 days immediately preceding study visit)  
Collect adjustment of medications and fluids if recorded  
Fistula closure (y/n)  
Complete Questionnaires (see additional documents)

IRB Study Number: 20170189  
Version Date: June 16, 2021  
PI: [name]

NCT02889393

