**Study Visit 11, Long-Term Follow-up Visit, 3 months after EOT (-2 weeks/+3 months)**

Monitor severe adverse events (SAE) and adverse events (AE)

Collect Concomitant medication review

Collect Nutritional Assessment

Chemistry Panel (sodium, potassium, chloride, bicarbonate, blood urea nitrogen, creatinine glucose)

Liver Function tests (total bilirubin, direct bilirubin, alkalkine phosphatase, alanine aminotransferase, aspartate aminotransferase, lipase, amylase)

Plasma PK (Pharmacokinetics)

- Processed according to separate "Sample Processing Procedure"

3-day average fistula volume (3 days immediately preceding study visit)

Fistula closure (y/n)

Complete Questionnaires (see additional documents)

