**Drug Administration, Dispensation and Disposition**

Once consent is obtained and necessary baseline data collected, the subject will begin receiving teduglutide (0.05 mg/kg/d, for moderate renal impairment defined as serum

IRB Study Number: 20170189  
Version Date: June 16, 2021  
PI: [name]

NCT02889393

creatinine > 1.5 times the upper limit of normal, the dose will be reduced to 0.025 mg/kg/d, administered once daily subcutaneously into the abdomen, thigh, or arm (at approximately the same time each day) for 8 weeks. For enrolled subjects demonstrating a favorable trend and are deemed to be reliable (both as determined by the PI) but still have a fistula at the end of treatment (EOT) or long-term follow-up, the subject will be offered an “open-label” extension whereby they will continue to receive teduglutide at the previous dose for up to another 12 months or permanent fistula closure, whichever occurs first.

Immediately prior to initiating the 8-week period of drug administration, the subject will receive training on how to safely reconstitute and administer the medication. The volume of reconstituted study drug to be administered is a fixed dose of 0.005 mL/kg body weight. Each day, the injection site should be changed. The subject should be dosed at approximately the same time each day. If a subject forgets to take drug, that day’s dose should be administered as soon as possible, even if this is later in the day or evening. Consecutive doses should be separated by approximately 12 hours. Dates of days with missed or incomplete doses are to be reported in the diary. The subject is going to be instructed to bring back all used and unused IP. The IP will then be disposed of per pharmacy SOP. University of Miami Research Pharmacy will be receiving, storing, dispensing, keeping inventory, and disposing the IP for this study as per their standard operating procedures.

Study drug will be packaged, labeled, and delivered to the clinical center by the sponsor or designee. Each study drug kit will contain labeling with the general dosage instructions, storage conditions, expiration date, kit number, and company name. All medication supplied to be used in this study will be manufactured, tested, labeled, and released according to current legal requirements and Good Manufacturing Practice (GMP). Ancillary supply kits containing syringes with needles for injection and reconstitution, sterile water, and alcohol swabs will also be provided.

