The Principle Investigator or designee will conduct an inventory upon receipt of the clinical supplies and will acknowledge receipt of the supplies to the sponsor. A copy of the shipping documents will be maintained for records. Study drug will be kept at controlled room temperature (15°-25°C, 59°-77°F) in a secure location until dispensed to the subject. Subjects will be instructed to keep study drug at controlled room temperature. The sterile water diluent should be stored at controlled temperature.

Study drug kits will be dispensed to subjects at each of the office visits during the 8 weeks of dosing and up to an additional 52 weeks of “open-label” extension at which the subject is required to be at the clinic. Each study drug kit is sufficient for a treatment period of 4 weeks (depending on visit #). The PI will keep a current record of the inventory and dispensing of all clinical supplies. This record will be made available to the sponsor’s monitor for the purpose of accounting for all clinical supplies. Any discrepancy or deficiency will be recorded, with an explanation. All supplies sent to the investigator will be accounted for and in no case will clinical supplies be used in an unauthorized situation.

IRB Study Number: 20170189  
Version Date: June 16, 2021  
PI: [name]

NCT02889393

Subject compliance will be checked at every visit (and telephone call) by asking the subjects if they have taken their study drug according to instructions and by reviewing the subject diary if available and to perform drug accountability. Compliance is considered to be achieved if the subject reports (by diary or discussion) 80% of the planned doses administered. The hierarchy of source documentation is the Diary as primary, and if not available then followed by study staff documentation of weekly visits and lastly documentation of monthly visits.

At present, the standard of care (SOC) for ECF involves source control treatment of intra-abdominal infection, nutritional support via enteral nutrition (EN), parenteral nutrition (PN), or oral intake, careful fluid and electrolyte management, and occasionally surgical repair. Subjects enrolled in this study will still receive SOC in addition to 8 weeks of teduglutide therapy and up to an additional 52 weeks of open-label extension when this applies.

Unless contraindicated by clinical condition, enrolled patients will undergo colonoscopy within 6 months prior to starting the drug.

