#### **Data Fields**

Age

BMI

Gender

Charlson Comorbidity Index

Questionnaires (see additional documents)

Cause of major intestinal resection: trauma, emergency operation, elective operation, inflammatory bowel disease, other

Location of fistula: stomach, duodenum, jejunum, ileum, colon

Days since last operation

Days since fistula diagnosis

Type of nutrition: per os (PO), enteral nutrition (EN), parenteral nutrition (PN), PO + EN, PO + TPN, EN + PN, PO +EN + PN

IRB Study Number: 20170189  
Version Date: June 16, 2021  
PI: [name]

NCT02889393

Concomitant medications: antidiarrheals, antisecretory agents  
3-day average fistula volume (continuous variable)  
Output of fistula >500 mL/day (Y/N)

Because of the expected increase in luminal absorption, subjects will be closely monitored for increased oral medication absorption, particularly opioids and sedating medications. Subjects will be assessed for pinpoint pupils and lethargy. If clinical evidence of increased oral medical absorption is discovered, the doses will be accordingly decreased. If clinical evidence of fluid overload is discovered (such as breathlessness, subjective dyspnea, new-onset pitting peripheral edema, change in body weight, jugular venous distention, and rales on lung auscultation), then EN and PN prescription will be decreased accordingly.

Additionally, subjects will be monitored for clinical evidence of volume depletion. Clinical signs suggestive of volume depletion include dry mucus membranes, poor skin turgor, decreased urine output, or rapid body weight loss.

Fluid and volume status will be assessed according to the usual clinical signs and symptoms: breathlessness, subjective dyspnea, new-onset pitting edema, change in body weight, and rales on lung auscultation. This will be assessed both in person at the time of study visit as well as by self report from the subject during phone calls.

Criteria for discontinuation of teduglutide in patients who experience fluid overload include: decrease in room-air oxygen saturation > 5% from baseline, significant worsening of peripheral edema resulting in functional limitation, severe dyspnea resulting in functional limitation, and hospitalization for congestive heart failure.

Data will be de-identified and stored on password-protected network accessible only to research staff. Data will be retained for at least six years following conclusion of the study on this network.

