**17) Confidentiality**

The protected health information collected for the purpose of this research study will be assigned a research code number and any obvious patient identifiers (name, social security number, hospital record number) will be removed from this information. Both the confidential health information and the information linking the research code numbers to the patients' identities will be stored in a secure manner (e.g., locked file cabinet, password protected database) accessible only to the research study personnel. The information linking the research code numbers to the patients' identities will be stored separate from the confidential health information.

Clinical data will be collected for no longer than one year after the patient has had the initial surgery. Data will be de-identified and stored on a password-protected network

IRB Study Number: 20170189  
Version Date: June 16, 2021  
PI: [name]

NCT02889393

accessible only to research staff. Data will be retained for at least six years following conclusion of the study on this network.

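### Data collection is capped at one year after an undefined initial surgery, which conflicts with the full 12-month extension and, for patients with older surgery, with the core visits

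*Combined protocol and SAP*

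**What the plan says.** Section 17 (Confidentiality) sets the limit: "Clinical data will be collected for no longer than one year after the patient has had the initial surgery". Retention is dealt with separately in the same paragraph (at least six years after the study ends), so this sentence governs collection only.

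Other sections bear on it as follows.

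- **Eligibility** (section 4, Inclusion criteria) admits an "Enterocutaneous fistula (ECF) that could be secondary to volvulus, injury, prior trauma or surgery, or vascular ischemia". Surgery is one possible cause among several, and no maximum interval since surgery is given.
- **Surgery in the study.** No operation is a study procedure. Section 5 (Drug Administration, Dispensation and Disposition) mentions it only as part of standard care: "careful fluid and electrolyte management, and occasionally surgical repair".
- **Time since surgery** is a recorded variable, listed in section 6 (Data Fields) as "Days since last operation". It counts from the last operation, not the initial one.
- **Core schedule** (section 5 and Appendix E). There are contacts every week to Visit 10 at Day 112 (plus or minus one week). Visit 11 follows three months after end of treatment (EOT), with a window of minus two weeks to plus three months.
- **Extension** (section 5 and Appendix E). Patients may enter at EOT or at long-term follow-up and continue "for up to another 12 months or permanent fistula closure, whichever occurs first". Monthly visits and alternating telephone contacts collect adverse events, medications and fistula volume.
- **Safety follow-up.** Section 9 records SAEs to 30 days after the last dose and follows adverse events unresolved at the end of treatment until they resolve or stabilize. Section 8 likewise follows persistently abnormal laboratory results and ongoing adverse reactions to resolution.

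**The concern.** The limit runs from an event that is outside the study, is undefined, and may lie at any distance before enrollment or may never have happened. The visits run from enrollment. Nothing links the two clocks, and no section exempts the study visits or the extension from the limit.

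Fistula volume is the primary endpoint, and quality of life at Visits 5, 10 and 11 is a named secondary endpoint. Safety data are required throughout the extension. Staff who follow the sentence must stop collecting required data for affected patients. Staff who follow the visit schedule exceed a limit stated in the protocol, and section 16 says that data will be audited against the protocol. With 10 planned subjects, losing even one or two patients' endpoint data would matter.

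**Working it through.** The limit cannot be derived from the schedule, so the check is calendar arithmetic. Assumptions: one year = 365 days, three months = about 91 days, and enrollment = Day 0.

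Let *s* be the number of days from the initial surgery to enrollment, with surgery first (*s* > 0). The last study day on which data may be collected is 365 − *s*.

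**Days the schedule requires**

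| Milestone | Nominal | Earliest | Latest |
|---|---|---|---|
| Visit 10 (EOT) | 112 | 112 − 7 = 105 | 112 + 7 = 119 |
| Visit 11 | 112 + 91 = 203 | 105 + 91 − 14 = 182 | 119 + 91 + 91 = 301 |
| Full extension entered at EOT | 112 + 365 = 477 | 105 + 365 = 470 | 119 + 365 = 484 |
| Full extension entered at Visit 11 | 203 + 365 = 568 | 182 + 365 = 547 | 301 + 365 = 666 |

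**Extension.** With surgery as late as the day of enrollment (*s* = 0), the limit falls on Day 365. A full extension from EOT overruns it by 477 − 365 = 112 days, and one from Visit 11 by 568 − 365 = 203 days. Even the earliest case overruns, by 470 − 365 = 105 days. Under nominal timing at most 365 − 112 = 253 extension days could be recorded. The 30-day SAE period after the last dose adds to each overrun.

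**Core visits.** A visit on day *d* may be recorded only if *s* ≤ 365 − *d*:

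- Day 56 (end of the first period): 365 − 56 = 309 days.
- Day 112: 365 − 112 = 253 days (246 to 260 across the window).
- Visit 11: 365 − 203 = 162 days nominally (365 − 301 = 64 to 365 − 182 = 183 across the window).
- Enrollment (Day 0): 365 days. Beyond that, nothing from enrollment on may be collected. Screening can precede enrollment by up to two months, so some screening data might still fall inside the limit.

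**What remains collectable at nominal timing.** There are 18 core contacts: enrollment, 16 contacts from Day 7 to Day 112, and Visit 11.

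| Surgery to enrollment, *s* (days) | Last collectable study day | Core contacts of 18 | Extension days from EOT |
|---|---|---|---|
| 0 | 365 | 18 | 253 |
| 90 | 275 | 18 | 163 |
| 162 | 203 | 18 | 91 |
| 180 | 185 | 17 | 73 |
| 253 | 112 | 17 | 0 |
| 309 | 56 | 9 | 0 |
| 365 | 0 | 1 | 0 |

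A patient with *s* between 254 and 309 days would have the first period complete and the Day 112 measurement missing, so the within-patient comparison that the cross-over is meant to give would lack its endpoint.

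**No prior surgery.** *s* does not exist, and the limit cannot be computed.

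**The case against.** The strongest reply is that the sentence has little practical force. It sits among de-identification and storage text. The operative instructions are the visit lists and Appendix E, and none of them refers to a stop tied to surgery. It may also be carried over from another protocol: the next section describes intubated and sedated patients in a crisis, while section 19b bars patients who cannot consent for themselves. That origin is an inference. It would explain the sentence but not remove the limit, which is current text with no exemption.

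Other parts of the reply stand, and they rule out stronger readings that a reader might infer.

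- **That no patient could complete a 12-month extension within the limit.** This does not hold for a patient with no surgery, for whom the limit never starts. If the undefined phrase meant a later repair operation, the limit might not bind either. The extension may also end early at permanent closure, and a short one can fit.
- **That core efficacy and safety data are lost across the board.** The loss depends on time since surgery, and the documents give no distribution of it. A patient enrolled soon after surgery can complete the nominal Visit 11 inside the limit.
- **That the sentence restricts use of the data, or that patients' authorization is exceeded.** The sentence limits collection. The consent pages are not in the documents reviewed, so whether they repeat the limit is unknown.

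**Conclusion.** The point holds as an internal contradiction. Section 17 ties data collection to an undefined event that need not have occurred, and the resulting limit is incompatible with the schedule.

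If the initial surgery preceded enrollment, the conflict with a full 12-month extension is certain under every visit window: the overrun is at least 105 days, and the extension may end as late as about Day 666. For the core study the conflict is conditional on time since surgery, with nominal cut-offs of about 253 days for Day 112 and 162 days for Visit 11. How many of the 10 patients would be affected cannot be determined from the documents.

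No sample size, significance level or analysis method changes. It should be corrected because, read literally, it forbids collecting required endpoint and safety data, and the correction costs almost nothing.

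**What to change.** Replace the sentence in section 17 with:

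*Clinical data will be collected from screening/consent through the last study visit (Visit 11 or the end of the open-label extension), including the SAE reporting period and any follow-up of unresolved adverse events or abnormal laboratory results required elsewhere in this protocol.*

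The closing clause is needed because sections 8 and 9 follow some events to resolution with no end date. A limit that stopped at the last visit plus the SAE period would cut those off. The change should leave the pre-consent eligibility screening under the partial HIPAA waiver requested in section 14 unaffected.

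The cost is one sentence in the protocol, plus matching wording in the consent and HIPAA text if the limit is repeated there. It adds no visits, measurements or patients and changes no treatment rule.

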### **18) Provisions to Protect the Privacy Interests of Subjects**

Access to patients and their protected health information along with the collection and analysis is necessary in order to conduct this research study. Consistent with the “minimum necessary standard” of the HIPAA privacy rule, we will only access and collect the specific health information necessary to complete this research study.

Some of the research investigators who will access and use the protected health information may also be involved directly in the care of the respective patients, thus obviating the privacy and confidentiality concerns.

Authorization to obtain protected health information will be obtained from the patient or their proxy as soon as possible. It is nearly impossible to provide authorization during a crisis situation in critical care areas during the workup of a critically ill patient. Generally, these patients are intubated, sedated, and hemodynamically compromised, especially during the initial days after admission.

The protected health information collected for the purpose of this research study will be assigned a research code number and any obvious patient identifiers (name, social security number, etc) will be removed from this information. Both the confidential health information and the information linking the research code numbers to the patients’ identities will be stored in a secure manner (e.g., locked file cabinet, password protected database) accessible only to the research study personnel.

### **19) Consent Process**

#### **19a. Remote Consenting will include the following:**

- Send a copy of the consent document via secure email or U.S. Mail.
- Arrange for a witness to attend and witness the consent discussion.
- Let the participant know that a witness will join the consent meeting.
- Set up a video meeting or 3-way call and send an invitation to the attendees.

We will ask the participant to scan or take a picture of each page of the documents and email the signed/dated documents to the study team. As an alternative, we may establish a secure network location for uploading the consent document.

During meeting:

- Identify everyone on the call.
- Review the informed consent with the participant, answer the participant’s questions and ask questions of the participant to confirm comprehension.
- Ask the participant if s/he consents to participate/continue participation.
- If the participant agrees, ask him/her to sign and date the consent document.
- If using 3-way call, ask the participant to confirm s/he signed & dated the document.

IRB Study Number: 20170189  
Version Date: June 16, 2021  
PI: [name]

NCT02889393

We will ask the participant to scan or take a picture of each page of the documents and email the signed/dated documents to the study team. As an alternative, the research could establish a "UM Box" location for uploading the consent document.

If the person is unable to take a picture, we will document the circumstances.

The person conducting the consent process will sign and date a copy of the consent document.

The witness will sign & date on the witness line of a copy of the consent document.

The person conducting the consent process will document the purpose for the remote consent (COVID-19), and each step of the process. The note will explain why the research team doesn't have the signed and dated document.

Documenting the Remote Consent process

The originals of the informed consent document signed by the investigator (and possibly the witness) will be placed in the participant's research record.

The person obtaining consent will document how s/he confirmed that the patient consented and signed the consent form. The note will include a statement indicating why the informed consent document signed by the participant was not retained, (e.g., due to contamination of the document by infectious material.)

If the participant cannot send a picture of the signed document, the person obtaining consent will document why a copy of the signed document is not available. See example below.

Example:

Informed consent was obtained on Date at Time. The participant could not come to the site for the consent process due to COVID-19 social distancing requirements. A copy of the consent document was emailed to the prospective participant before the consent discussion

The consent process was performed by phone/ZOOM. The individuals attending the discussion were: (list the names of the individuals). The person obtaining consent explained the research to the participant and answered the participant's questions. The person obtaining consent asked the participant questions to ascertain whether the s/he understood the study, and the participant was able to answer the questions. The participant voluntarily agreed to participate. The subject/LAR signed and dated the consent document. The research was not able to obtain a copy of the signed original

IRB Study Number: 20170189  
Version Date: June 16, 2021  
PI: [name]

NCT02889393

consent document because consent was obtained remotely, and the document may transmit the COVID-19 infection.

After signing the consent document, the participant took a picture and sent it to the research team/ OR The participant was unable to send a picture of the document. A witness observed the entire process.

The consentor will then add similar documentation about the HIPAA authorization.

